6.0 Adverse Events

The investigator will monitor each subject for clinical and laboratory evidence of adverse events on a routine basis throughout the study. The investigator will assess and record

any adverse event in detail including the date of onset, event diagnosis (if known) or sign/symptom, severity, time course, outcome, relationship of the adverse event to study drug, and any action(s) taken. For serious adverse events not considered "probably related" to study drug, the investigator will provide an Other cause of the event. For adverse events to be considered intermittent, the events must be of similar nature and severity. Adverse events, whether in response to a query, observed by site personnel, or reported spontaneously by the subject will be recorded.

All adverse events will be followed to a satisfactory conclusion.

6.1 Definitions

6.1.1 Adverse Event

An adverse event (AE) is defined as any untoward medical occurrence in a patient or clinical investigation subject administered a pharmaceutical product and which does not necessarily have a causal relationship with this treatment. An adverse event can therefore be any unfavorable and unintended sign (including an abnormal laboratory finding), symptom, or disease temporally associated with the use of a medicinal (investigational) product, whether or not the event is considered causally related to the use of the product.

Such an event can result from use of the drug as stipulated in the protocol or labeling, as well as from accidental or intentional overdose, drug abuse, or drug withdrawal. Any worsening of a pre-existing condition or illness is considered an adverse event.

Laboratory abnormalities and changes in vital signs are considered to be adverse events only if they result in discontinuation from the study, necessitate therapeutic medical intervention, meets protocol specific criteria (see Section 6.7 regarding toxicity management) and/or if the investigator considers them to be adverse events.

An elective surgery/procedure scheduled to occur during a study will not be considered an adverse event if the surgery/procedure is being performed for a preexisting condition and the surgery/procedure has been pre planned prior to study entry. However, if the pre-existing condition deteriorates unexpectedly during the study (e.g., surgery performed

earlier than planned), then the deterioration of the condition for which the elective surgery/procedure is being done will be considered an adverse event.

Hospitalization for the purpose of TLS prophylaxis (e.g., for I.V. hydration) will not be captured as a serious adverse event (SAE), unless there is an additional reason for hospitalization or an additional criterion for seriousness other than hospitalization.

A treatment-emergent adverse event is defined as any adverse event with onset or worsening reported by a subject from the time that the first dose of study drug is administered until 30 days have elapsed following discontinuation of study drug administration.

6.1.2 Serious Adverse Events

If an adverse event meets any of the following criteria, it is to be reported to AbbVie as a serious adverse event (SAE) within 24 hours of the site being made aware of the serious adverse event.

Death of Subject	An event that results in the death of a subject.
Life-Threatening	An event that, in the opinion of the investigator, would have resulted in immediate fatality if medical intervention had not been taken. This does not include an event that would have been fatal if it had occurred in a more severe form.
Hospitalization or Prolongation of Hospitalization	An event that results in an admission to the hospital for any length of time or prolongs the subject's hospital stay. This does not include an emergency room visit or admission to an outpatient facility.
Congenital Anomaly	An anomaly detected at or after birth, or any anomaly that results in fetal loss.
Persistent or Significant Disability/Incapacity	An event that results in a condition that substantially interferes with the activities of daily living of a study subject. Disability is not intended to include experiences of relatively minor medical significance such as headache, nausea, vomiting, diarrhea, influenza, and accidental trauma (e.g., sprained ankle).

Important Medical Event Requiring Medical or Surgical Intervention to Prevent Serious Outcome	An important medical event that may not be immediately life-threatening or result in death or hospitalization, but based on medical judgment may jeopardize the subject and may require medical or surgical intervention to prevent any of the outcomes listed above (i.e., death of subject, life-threatening, hospitalization, prolongation of hospitalization, congenital anomaly, or persistent or significant disability/incapacity). Examples of such events include allergic bronchospasm requiring intensive treatment in an emergency room or at home, blood dyscrasias or convulsions that do not result in inpatient hospitalization, or the development of drug dependency or drug abuse.
Spontaneous Abortion	Miscarriage experienced by study subject.
Elective Abortion	Elective abortion performed on study subject.

6.2 Adverse Event Severity

The investigator will rate the severity of each adverse event according to the National Cancer Institute Common Terminology Criteria for Adverse Events, Version 3.0 (NCI CTCAE).³⁴

If a reported adverse event increases in severity the initial adverse event should be given an outcome date and a new adverse event reported to reflect the change in severity. For all reported serious adverse events that increase in severity, the supplemental eCRFs (paper CRFs for the Extension Study) also need to be updated to reflect the change in severity.

For adverse events not captured by the Common Terminology Criteria, the following should be used:

Grade 1 (Mild)	The adverse event is transient and easily tolerated by the subject.
Grade 2 (Moderate)	The adverse event causes the subject discomfort and interrupts the subject's usual activities.

Grade 3/4 (Severe) The adverse event causes considerable interference with the subject's usual activities and may be incapacitating or life-threatening.

Grade 5 The adverse event resulted in death of the subject.

6.3 Relationship to Study Drug

The investigator will use the following definitions to assess the relationship of the adverse event to the use of study drug:

Probably Related An adverse event has a strong temporal relationship to study drug or recurs on re-challenge and an Other cause of event is unlikely or significantly less likely.

Possibly Related An adverse event has a strong temporal relationship to the study drug and an Other cause of event is equally or less likely compared to the potential relationship to study drug.

Probably Not Related An adverse event has little or no temporal relationship to the study drug and/or a more likely Other cause of event exists.

Not Related An adverse event is due to an underlying or concurrent illness or effect of another drug and is not related to the study drug (e.g., has no temporal relationship to study drug or has a much more likely Other cause of event).

For causality assessments, events meeting the categories of probably or possibly will be considered "associated." Events that are probably not or not related will be considered "not associated." In addition, when the investigator has not reported a causality or deemed it not assessable, AbbVie will consider the event associated.

If an investigator's opinion of possibly, probably not, or not related to study drug is given, an Other cause of event must be provided by the investigator for the serious adverse event.

6.4 Adverse Event Collection Period

[figure not shown]
All serious and non-serious adverse events reported from the time of study drug administration until 30 days following discontinuation of study drug administration will be collected, whether elicited or spontaneously reported by the subject.

Serious adverse events occurring after the study-specific informed consent is signed but prior to the initial dose of the investigational product will be collected only if they are considered by the investigator to be causally related to the study required procedures.

For subjects in the Extension Study, all adverse events that occur after Day 1 visit in the Extension Study should be captured in the Extension Study paper Case Report Forms.

Adverse event information will be collected as shown in [Figure 5](#).

Figure 5. Adverse Event Collection

* Only if considered by the investigator to be causally related to study required procedures.

6.6 Pregnancy

In the event of a positive pregnancy test, subjects must immediately discontinue study drug and must be discontinued from the study. The investigator must report the positive pregnancy test to the appropriate contact listed in protocol Section 6.5 within 1 working day of the site becoming aware of the pregnancy.

Information regarding a pregnancy occurrence in a study subject and the outcome of the pregnancy will be collected. The investigator must follow the pregnancy to completion and provide an update to AbbVie after delivery.

Male subjects should be informed that contraceptive measures should be taken by their female partners. If the subject's partner should become pregnant during the study, this should also be reported and data may be collected.

Pregnancy in a study subject is not considered an adverse event. However, the medical outcome of an elective or spontaneous abortion, stillbirth or congenital anomaly is considered a serious adverse event and must be reported to AbbVie within 24 hours of the site becoming aware of the event.

6.7 Toxicity Management

6.7.1 Definition - Dose Limiting Toxicity

Dose-limiting toxicities for dose-escalation purposes will be determined during the first cycle. Adverse events occurring following the first cycle will also be evaluated by

the investigator and the AbbVie Medical Monitor and may be considered as dose limiting. Any of the following events, which are considered possibly or probably related to the administration of ABT-263, will be considered a dose limiting toxicity (DLT).

- Thrombocytopenia:
 - Grade 4 thrombocytopenia ($< 25,000/\text{mm}^3$)
- Platelet counts $< 25,000/\text{mm}^3$ should be confirmed the same day by manual reading and a separate peripheral draw. If the repeat platelet count is $\geq 25,000/\text{mm}^3$, this will not be considered a DLT. If the repeat platelet count cannot be obtained within the same day as the initial measurement of $< 25,000/\text{mm}^3$, then the initial measurement will constitute a DLT.
- Grade 2 or higher bleeding associated with thrombocytopenia
- All other Grade 3, 4 or 5 adverse events will be considered a DLT. Exceptions include:
 - Grade 3, 4 Afebrile Neutropenia less than 7 days
 - Grade 3, 4 Leukopenia
 - Grade 3, 4 Lymphopenia
 - Grade 3 nausea, vomiting and/or diarrhea unless unresponsive to treatment
 - Grade 2 toxicity that requires dose modification or delay of > 1 week, will be considered a DLT (e.g., peripheral neuropathy)

Any DLT will require an interruption and possible discontinuation of ABT-263. ABT-263 may be reintroduced, but only at a reduced dose, if the toxicity grade returns to \leq Grade 1 or to baseline if Grade 2 at study entry. Following a DLT of thrombocytopenia, ABT-263 may be reintroduced, but only at a reduced dose, if the platelet toxicity grade returns to \leq Grade 2 ($\geq 50,000/\text{mm}^3$). Any reduced dose level will be jointly defined by the investigator and the AbbVie Medical Monitor. The dose may be increased thereafter upon joint determination of the investigator and the AbbVie Medical Monitor. This dose is not to exceed the highest tolerated dose level.

For the Phase 1 portion of the study, all decisions regarding continued dosing for individual subjects will be medically managed by the investigator, in conjunction with the

AbbVie Medical Monitor, as appropriate. These decisions will be driven by the definition of DLTs as described above.

6.7.2 Management of Thrombocytopenia

ABT-263 induces apoptosis, rather than lysis, of circulating platelets, which differs from typical chemotherapy induced thrombocytopenia related to myelosuppression.

All decisions regarding continued ABT-263 dosing for individual subjects will be determined by the investigator, in conjunction with the AbbVie Medical Monitor, as appropriate. These decisions should be guided by the following:

Administration of ABT-263 will be interrupted or discontinued for:

- Any pre-dose platelet count $< 25,000/\text{mm}^3$
- Any clinically significant bleeding, defined as Grade 2 or higher hemorrhage

If ABT-263 is held, it may be restarted, but only at a reduced dose to be jointly defined by the investigator and the AbbVie Medical Monitor, once the subject's platelet count is $\geq 50,000/\text{mm}^3$. The dose may be increased (not to exceed the highest tolerated dose) thereafter upon joint determination of the AbbVie Medical Monitor and the investigator.

After any Grade 4 platelet count $< 25,000/\text{mm}^3$ is observed for the first time in a subject, serial PK samples will be collected. PK samples will be collected as soon as possible after the Grade 4 platelet count is determined and then 24 and 48 hours after the event. Starting with Protocol Amendment 13, PK samples will NOT be collected.

Limited human clinical data are available to understand the response to infusion of exogenous platelets in the presence of circulating drug levels. Platelet transfusion studies conducted in beagle dogs demonstrated that transfusion of one-day old platelets administered near the time of ABT-263 C_{max} , resulted in higher platelet levels than dogs not receiving supplemental platelets. Platelet concentrations remained higher after 24 hours with declining ABT-263 concentrations. This study suggests that infusion of

platelets may have beneficial effects in treating acute thrombocytopenia following oral dosing with ABT-263.

If platelet transfusions are required in response to active bleeding, dosing of ABT-263 should be suspended. It should be noted that platelet response with transfusions may not follow typical platelet kinetics of thrombocytopenia as with typical chemotherapy induced myelosuppression. Procedures consistent with local institutional blood banking guidelines regarding platelet transfusions should be followed.

Platelet Transfusion Recommendations:

If a platelet transfusion is deemed necessary, the treating physician should be aware of the following:

- Due to the rapid apoptotic effect of ABT-263 on mature platelets, the initial increase in platelets post-transfusion may be smaller and the duration of response may be shorter. For this reason, donor platelets collected as recently as possible prior to transfusion should be considered.
- A post-transfusion platelet count should be obtained within 10 to 60 minutes.
- Additional transfusions may be necessary to achieve the desired platelet response.

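### Sections 6.7.1 and 6.7.2 set different restart conditions after a hold for Grade 2 or higher bleeding, and neither refers to the other

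*Protocol*

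**What the plan says.** Protocol Section 6.7.2 interrupts or discontinues drug for two reasons. One is a pre-dose platelet count below 25,000/mm³. The other is "Any clinically significant bleeding, defined as Grade 2 or higher hemorrhage", with no condition on platelet count or on relatedness to drug. One restart sentence serves both: "If ABT-263 is held, it may be restarted, but only at a reduced dose to be jointly defined by the investigator" and the Medical Monitor, "once the subject's platelet count is" at least 50,000/mm³. That sentence does not mention bleeding. The section presents its criteria as guides to decisions made by the investigator with the Medical Monitor. It also suspends dosing when active bleeding requires platelet transfusion, but gives no separate restart condition for that case.

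Protocol Section 6.7.1 defines DLTs as listed events "which are considered possibly or probably related to the administration of ABT-263". The list includes "Grade 2 or higher bleeding associated with thrombocytopenia". After any DLT, "ABT-263 may be reintroduced, but only at a reduced dose, if the toxicity grade returns to" Grade 1 or less, or to baseline for a subject who entered at Grade 2. A further sentence has a narrower scope: "Following a DLT of thrombocytopenia, ABT-263 may be reintroduced, but only at a reduced dose, if the platelet toxicity grade returns to" Grade 2 or less, which the protocol equates with at least 50,000/mm³.

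Neither section refers to the other on restart.

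**The concern.** Bleeding is the clinical harm that the platelet rules are there to prevent. For a subject held because of a bleed, one section tests only the platelet count and the other, read literally, tests only the grade of the toxicity. An investigator who consults one section can reach a different answer from an investigator who consults the other.

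What is at stake is the timing of re-exposure, and through it the length of the hold. Section 5.4.1 lists toxicity requiring an interruption of more than 3 weeks among the reasons for discontinuation, so the choice of section could bear on whether a subject stays on study.

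**Working it through.** There is no stated figure to reproduce. The check sets the two rules side by side.

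**Which bleeds fall under both sections.** Section 6.7.2 covers any Grade 2 or higher hemorrhage. Section 6.7.1 covers drug-related bleeds by three routes:

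- Grade 2 or higher bleeding with thrombocytopenia.
- Other Grade 3 to 5 events.
- Grade 2 toxicity that needs a dose modification or a delay of more than one week.

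The third route matters because 6.7.2 permits restart only at a reduced dose, which is a dose modification. The overlap is therefore wide.

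**The grid.** Take a bleeding DLT with the bleeding item read as separate from thrombocytopenia, as it appears in the extracted text. Cross bleeding status with platelet band.

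| Bleeding now | Platelets (/mm³) | 6.7.1 restart condition | 6.7.2 restart sentence |
|---|---|---|---|
| Grade 2 or higher | below 25,000 | not met | not met |
| Grade 2 or higher | 25,000 to below 50,000 | not met | not met |
| Grade 2 or higher | 50,000 or more | **not met** | **met** |
| Grade 1 or less | below 25,000 | not met (thrombocytopenia DLT) | not met |
| Grade 1 or less | 25,000 to below 50,000 | **met** | **not met** |
| Grade 1 or less | 50,000 or more | met | met |

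The restart sentences disagree in 2 of the 6 rows, and in opposite directions.

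**Row 3.** A related Grade 2 bleed at 60,000/mm³ meets the 6.7.2 restart count on the day of the hold. It can still be bleeding with thrombocytopenia, because 6.7.1 itself treats counts of 50,000/mm³ and above as platelet toxicity of Grade 2 or less. The 6.7.2 hold trigger also remains true while the bleed stays at Grade 2 or higher. Within 6.7.2, then, the trigger and the restart sentence point different ways, and the text does not say which prevails.

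**Row 5.** A bleed resolves while the count stays at 30,000/mm³. The general sentence in 6.7.1 allows reintroduction and 6.7.2 does not. This is foreseeable: Section 5.2.5 admits subjects to the Extension with untransfused counts from 25,000/mm³ upward, provided that counts of 50,000/mm³ or less are stable.

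**Alternative layout.** If the bleeding item is nested under thrombocytopenia on the page, the platelet sentence in 6.7.1 arguably governs. Row 5 becomes not met in both sections and row 3 becomes met in both. The sections then agree on platelets, but neither of those restart sentences mentions the bleeding having resolved.

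**The case against.** The strongest reply is that both rules are permissive. Each says that drug may be resumed when its condition holds, and neither says that its condition is enough regardless of the other section. A site that satisfies both breaches neither: in row 3 it waits for the bleed to resolve, and in row 5 it waits for the count. That is correct, and it makes this a missing link between two rules and not a flat contradiction. But nothing in the protocol tells a site to apply both.

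A second reply is that the investigator decides with the Medical Monitor, and that the reduced dose is jointly defined. This lowers the practical risk. It does not remove the mismatch, because the criteria meant to guide those decisions differ.

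A reader might also draw three stronger conclusions that the documents do not support:

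- **That the plan permits restart while a subject is still bleeding.** The 6.7.2 hold trigger is not limited to onset, so an ongoing Grade 2 or higher bleed still calls for a hold. Bleeding that needs transfusion separately suspends dosing.
- **That a Grade 2 bleed without thrombocytopenia is governed by 6.7.2 alone.** If it is related to drug, it can also be a DLT through the dose-modification or delay item in 6.7.1.
- **That hold length changes who is evaluable under the 80% dosing rule.** Section 5.4.1 lists experiencing a DLT as its own ground for evaluability, so a subject with a bleeding DLT counts whatever the hold length.

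**Conclusion.** The point holds as a mismatch between two safety rules. After a hold for Grade 2 or higher bleeding, 6.7.2 names only a platelet count, 6.7.1 names toxicity grade with a platelet condition reserved for thrombocytopenia DLTs, and the two are not linked. The restart sentences disagree in two of six combinations of bleeding status and platelet band. The documents give no count of such holds, so the number of subjects affected cannot be stated.

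The conclusion rests on these assumptions:

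- Row 5 needs the bleeding item to stand apart from thrombocytopenia, which should be checked against the page layout. It also takes a count of 25,000 to below 50,000/mm³ not to be a thrombocytopenia DLT in itself; under that heading 6.7.1 names only Grade 4.
- After Cycle 1, 6.7.1 leaves it to the investigator and the Medical Monitor whether an event counts as dose limiting. Its restart condition then applies where they judge that it does.
- The 3-week criterion in 5.4.1 operates through the investigator's judgment, so hold length can bear on discontinuation but does not determine it.

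The SAP (Data Sets Analyzed) reports 29 Phase 1 and 31 Phase 2 subjects already enrolled and treated, 29 + 31 = 60 in all. The remaining effect is therefore mainly in the Extension, which Section 5.1 puts at approximately 13 subjects.

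**What to change.** Reconcile Sections 6.7.1 and 6.7.2. State one restart condition for a hold due to Grade 2 or higher bleeding in one section, and cross-refer to it from the other. The text should say how bleeding grade and platelet count each enter the condition, for bleeding with and without thrombocytopenia. It should also make plain whether the bleeding item in 6.7.1 belongs to the thrombocytopenia group. Which values and conditions apply is the sponsor's clinical decision.

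The cost is a short wording change in a protocol amendment. It adds no procedures or subjects.

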6.7.3 Management of Lymphopenia

There is a potential for clinically significant lymphopenia in this study. If clinically indicated, anti-infective prophylaxis should be implemented at the investigator's discretion, including appropriate prophylaxis for viral, fungal, bacterial or *Pneumocystis carinii* pneumonia (PCP) infections. Potential for drug-drug interactions should be considered. See [Appendix E](#) for a description of excluded and cautionary medications.

6.7.4 Management of Tumor Lysis Syndrome

There is a potential for tumor lysis in subjects with various tumor types in the presence of the following risk factors: bulky disease, elevated pre-treatment LDH levels, elevated

leukocyte count and dehydration. Adequate hydration, careful monitoring of laboratory values and an agent to reduce the uric acid level should be considered for subjects at high risk during the Lead-in and subsequent cycles. Please discuss with the AbbVie Medical Monitor, as appropriate.

